5.1 Variables

Corporate Confidential Information

If data permit and as applicable, the following pharmacokinetic parameters for the parent LLG783 will be determined using the actual recorded sampling times and non-compartmental method(s) with Phoenix WinNonlin (Version 6.4 or higher) from the serum concentration data.

- PK parameters related to secondary objectives:
 - AUC_{inf}, AUC_{last}, AUC_{0-t}, AUC_{0tau}, C_{max}, T_{max}.

Corporate Confidential Information

5.2 Descriptive analyses

LLG783 serum concentrations will be listed by treatment, subject, and visit/sampling time point. Descriptive summary statistics will be provided by treatment and visit/sampling time point, including the frequency (n, %) of concentrations below the LLOQ (and above the ULOQ) and reported as zero. Pharmacokinetic parameters will be listed by treatment and subject and summarized by treatment and visit. Summary statistics will include mean (arithmetic and geometric), SD, CV (arithmetic and geometric), median, minimum and maximum. An exception to this is T_{max} where median, minimum and maximum will be presented.

Concentrations below LLOQ will be treated as zero in summary statistics and for PK parameter calculations. A geometric mean will not be reported if the dataset includes zero values.

Arithmetic mean (SD) serum concentration by time will be plotted on linear-linear and log-linear scale (all treatment groups in the same graph).

Overlaying individual serum concentration by time profile, by treatment will be plotted (one graph per treatment group, all subjects in the same graph) on linear-linear and log-linear scale.

Individual serum concentration by time profile, by subject will be plotted on linear-linear and log-linear scale (one graph per treatment group and subject).

6 Statistical methods for Efficacy/Pharmacodynamic (PD) parameters

All subjects within the PD analysis set will be included in the PD data analysis.

In case of dose adjustment occurring during the study, subjects will be analyzed under first doses received, censoring any observations post dose adjustment (if any) in statistical models and descriptive summaries.

6.1 Primary objective

To evaluate the effect of LLG783 on functional capacity after 3 months of treatment in subjects with PAD and intermittent claudication.

6.1.1 Variables

The primary efficacy endpoint is the Maximum walking distance (MWD) defined as the total distance walked in 6 minutes as assessed by the 6MWT and will be used to evaluate functional capacity of PAD subjects participating in this study.

Change from baseline in MWD will also be derived. Baseline will be taken from the screening 6-minute walk test.

6MWT data will be excluded from primary and secondary analyses under below conditions:

- within 24 hours after narcotic pain medication
- the very first 6MWT after the adverse event of COPD exacerbation
- all tests after post baseline stent or angioplasty procedures
- Lap distance for the 6MWT significantly shorter than the recommended length of 50-70m

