3.1 Study design

Figure 3-1 Study Design

This is a non-confirmatory, randomized, patient and investigator-blinded, placebo-controlled, parallel-group study in patients with PAD and intermittent claudication. Approximately 40 randomized patients will be treated in a 1:1 ratio to receive LLG783 or placebo as an i.v. infusion of CCI i.v. dosing once every 4 weeks for a total of 4 doses over a period of 12 weeks/3 months. Key study assessments are conducted at week 16 (month 4) of the study (i.e. after 16 weeks of exposure), which is one month after the final dose of study medication.

The dose may be altered based on review of data from the 1st interim analysis (IA).

Corporate Confidential Information

Potential study participants will undergo screening assessments, including 6MWT and ABI, to determine eligibility. Patients who pass the screening evaluations will come to the investigational site on Day 1, at which time inclusion and exclusion criteria will be re-reviewed, and eligible patients will be randomized and dosing will commence.

Assessments of functional capacity (6MWT) will be made at weeks 8 and 16 (days 57 and 113) following the first dose of study medication, with follow-up functional assessments at weeks 24 and 32 (days 169 and 225) following the first dose of study medication (i.e. 2 and 4 months following the last dose of medication, see [Figure 3-1](#)). These follow-up assessments will be performed to help define durability of clinical response as LLG783 exposure declines. The primary endpoint of improved walk distance will be adjudicated based on the 8 and 16 week data points, though the 24 and 32 week data may be used in final statistical modeling.

Safety assessments will include physical examinations, ECGs, vital signs, standard clinical laboratory evaluations (hematology, blood chemistry, and urinalysis), as well as AE and SAE monitoring.

Patients who discontinue the study for reasons other than safety prior to the week 16 visit may be replaced in order to ensure ability to assess 40 patients with a functional assessment after 16 weeks of exposure.

Corporate Confidential Information

Corporate Confidential Information

Corporate Confidential Information

Corporate Confidential Information

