3.7.1 Blood sample volumes

A maximum of 500 mL of blood is planned to be collected over a period of approximately 35 weeks, from each patient as part of the study. Additional samples may be required for safety monitoring.

Timings of blood sample collection are outlined in the Assessment Schedule ([Section 8.1](#)).

A summary blood log is provided in the SOM. Instructions for sample collection, processing, storage and shipment information is available in the Central Laboratory Manual.

Corporate Confidential Information

4 Population

Approximately 40 patients with PAD and intermittent claudication will be randomized into the study to be treated with 4 i.v. doses of study medication vs. placebo.

Replacement patients will be enrolled to replace those patients who discontinue the study for reasons other than safety before their 16-week 6MWT visit. This includes patients who, for clinical reasons, require an interventional procedure (e.g. angioplasty, stenting, or bypass surgery) after randomization, but before the 16 week (day 113) visit.

Corporate Confidential Information

The Investigator must ensure that all patients being considered for the study meet the following eligibility criteria. No additional criteria should be applied by the investigator, in order that the study population will be representative of all eligible patients.

Patient selection is to be established by checking through all eligibility criteria at screening.

This criteria should be re-reviewed at the time of their Day 1 visit prior to the administration of the first dose. A relevant record (e.g. checklist) of the eligibility criteria must be stored with the source documentation at the study site.

Deviation from any entry criterion excludes a patient from enrollment into the study.

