 - h. Uncontrolled diabetes as defined by a random fasting glucose level of 13 mmol/L or 240 mg/dL or a HbA1c greater than 9% as measured at screening. Diabetes should be treated as appropriate during the study.
6. Any of the following concomitant hepatic or renal conditions or diseases:
 - a. Patients with severe renal impairment defined as eGFR < 15 mL/min/1.73m² [as calculated by the MDRD (Modification of Diet in Renal Disease) method] or those receiving current or planned dialysis or ultrafiltration.
 - b. Known active or recurrent hepatic disorder (including cirrhosis, hepatitis B and hepatitis C - including positive hepatitis B surface antigen or hepatitis C test), or alanine aminotransferase/aspartate aminotransferase (ALT/AST) levels > 2.5 times upper limits of normal (ULN) or total bilirubin > 2 times ULN at screening.
7. History of any of the following chronic conditions:
 - a. Malignancy of any organ system (other than localized basal or squamous cell carcinoma of the skin), treated or untreated, within the past **3 years**, regardless of whether there is evidence of local recurrence or metastases.
 - b. Hemoglobin levels < 10.6 g/dL at screening.

- c. History of immunodeficiency diseases, including a positive HIV (ELISA and Western blot) test result.
 - d. History of any hypercoagulable or bleeding disorders.
8. Major surgical procedure (such as coronary artery bypass grafting, carotid endarterectomy, abdominal surgery) \leq 6 months before screening (\leq 4 weeks before screening for coronary stent placement or angioplasty) or planned coronary revascularization or any other major surgical procedure planned to occur during the planned time frame of the study. Patients who have undergone peripheral vascular interventions $>$ 6 months prior to screening may still be considered eligible, provided they meet all other inclusion/exclusion criteria. Patients with actively planned/scheduled lower extremity peripheral vascular interventions within the first 4 months after enrollment should not be enrolled. However, if clinically indicated during the study, a patient may undergo peripheral vascular intervention.
 9. Any surgical or medical condition that in the opinion of the Investigator may place the patient at higher risk from his/her participation in the study.

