6.10 Rescue medication

There is currently no specific recommendation for rescue medication for this compound, but standard-of-care medications for AEs should be administered at PI discretion. See [Section 6.9](#) for recommended treatment of AEs.

If clinically indicated during the study, a patient may undergo peripheral vascular intervention for treatment of their underlying PAD (see details for exclusion criteria related to interventions in [Section 4.2](#)).

Use of concomitant medication or therapy must be recorded on the Concomitant medications/Significant non-drug therapies CRF.

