11.4.3 Handling of missing values/censoring/discontinuations

The primary analysis will be based on all patients with a baseline MWD and at least one post-baseline MWD. Patients who undergo any lower extremity vascular interventions (angioplasty, stenting, or bypass surgery) before the Week 16 efficacy assessment or patients who drop out for other reasons before this assessment may be replaced to ensure 40 patients complete this primary endpoint assessment. Data from such patients will be included in the model for the primary analysis until the time of dropout or intervention; no imputation of the missing data will be performed for the primary analysis.

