6.1.3.1 Model checking procedures

Handling of missing values/censoring/discontinuations

The primary analysis will be based on all subjects with a baseline MWD and at least one post baseline MWD. Subjects who undergo any lower extremity vascular interventions (angioplasty, stenting, or bypass surgery) before the Week 16 efficacy assessment or subjects who drop out for other reasons before this assessment may be replaced to ensure 40 subjects complete this primary endpoint assessment. Data from such subjects will be included in the model for the primary analysis until the time of dropout or intervention; no imputation of the missing data will be performed for the primary analysis.

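### SAP 6.1.1 drops walks after a late leg stent or angioplasty but not after a late leg bypass, so only the latter stay in the Week 24 and 32 estimates

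*SAP*

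**What the plan says.** Two rules decide which six-minute walks are dropped after a vascular procedure.

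- **SAP 6.1.1 (Variables)** excludes "all tests after post baseline stent or angioplasty procedures" from primary and secondary analyses. It sets no time limit, does not name bypass and does not say which arteries are meant. SAP 6.2.1 carries the same list to pain-free walking distance.
- **SAP 6.1.3.1** speaks of "Subjects who undergo any lower extremity vascular interventions (angioplasty, stenting, or bypass surgery) before the Week 16 efficacy assessment". It allows replacement of these subjects and then adds: "Data from such subjects will be included in the model for the primary analysis until the time of dropout or intervention". Protocol 11.4.3 has the same rule for "Patients who undergo any lower extremity vascular interventions (angioplasty, stenting, or bypass surgery) before the Week 16 efficacy assessment".

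Protocol section 4 (Population) also groups the three procedures when it describes replacement of patients who "require an interventional procedure (e.g. angioplasty, stenting, or bypass surgery) after randomization, but before the 16 week (day 113) visit".

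On whether a late bypass can occur, exclusion criterion 8 in protocol 4.2 bars "any other major surgical procedure planned to occur during the planned time frame of the study". Protocol 6.10 allows unplanned cases: "If clinically indicated during the study, a patient may undergo peripheral vascular intervention for treatment of their underlying PAD".

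Walks are scheduled at Weeks 8, 16, 24 and 32. Of the last two, protocol 3.1 says: "These follow-up assessments will be performed to help define durability of clinical response as LLG783 exposure declines". It makes their use in the final modelling optional. SAP 6.1.3 estimates the treatment difference, p-value and 80% interval at each visit and sets no cut at Week 16. It takes both decision criteria from Week 16.

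**The concern.** Having decided to discard walks made after revascularisation, the plan does so unevenly. After Week 16, a patient who has a leg stent or angioplasty loses the later walks, and a patient who has a leg bypass keeps them. Neither document explains the difference, and wherever else the three procedures are listed they are listed together. It reads as an omission.

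Weeks 24 and 32 exist to show whether any response lasts as drug exposure falls. A change in walking caused by surgery would be counted there as drug or placebo response. The same change after a late stent would not be counted. The maximum-change regression in SAP 6.1.3.3 names no visit limit, so a retained post-bypass walk could also become a patient's maximum.

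**Working it through.** **The rules side by side, for leg procedures after baseline**

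| Procedure | Before the Week 16 assessment | After the Week 16 assessment |
|---|---|---|
| Stent or angioplasty | Later walks removed (SAP 6.1.1 and 6.1.3.1) | Later walks removed (SAP 6.1.1) |
| Bypass | Later walks removed (SAP 6.1.3.1) | Later walks kept (neither rule applies) |

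Nothing else fills the last cell. SAP Table 4-1 has no deviation code for an on-study intervention. A clinically indicated intervention is permitted, so it is not a deviation that would remove the patient from the PD set. The LOCF and WOCF analyses act on missing values, and these walks are observed.

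**Size.** The plan states no figure on this point to reproduce. About 40 patients allocated 1:1 gives 20 per arm (protocol 3.1, SAP 1.4). The size of the change, the SD and the correlation below are assumptions.

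1. *Shift in one arm's mean* = change / n. One patient: 100/20 = 5.0 m; 150/20 = 7.5 m. Two patients in the same arm: 10 to 15 m. None: 0.
2. *Half-width of the 80% interval for the difference* = SD × √(2/20) × t(0.90; 37 df), with t = 1.305. SD 50 m: 50 × 0.3162 × 1.305 = 20.6 m. SD 80 m: 80 × 0.3162 × 1.305 = 33.0 m. A shift of 5.0 to 7.5 m is therefore between 5.0/33.0 = 15% and 7.5/20.6 = 36% of the half-width.
3. *Generalised least squares fit of the SAP model* with one common baseline slope, SD 70 m, correlation 0.5 or 0.7 between visits, and 100 m added at Weeks 24 and 32 for one LLG783 patient:
   - All walks present: the difference moves by +4.6 to +4.8 m at Weeks 24 and 32, and by −0.2 to −0.4 m at Week 16. The small Week 16 move comes through the shared baseline slope; with the optional visit-by-baseline term it is 0.0 m.
   - That patient's Week 16 walk missing: Week 16 moves by +2.2 to +2.5 m, because the model predicts the missing walk partly from the later ones.
   - A 100 m loss gives the same figures with the sign reversed, as does a gain in a placebo patient.
   - Bypass after day 169: only Week 32 is affected. Week 24 moves by 0.0 m with the visit-by-baseline term.
4. *Simulation of keeping against excluding the walks* (REML, unstructured covariance, SD 50, 60 or 80 m, correlation 0.5 or 0.7, one LLG783 patient gaining 100 or 150 m at both late visits, Week 16 walk present, 200 runs in each of 24 settings): the median move in the Week 24 or 32 difference was 4.0 to 7.9 m across settings. At Week 16 it was 0.0 m with the visit-by-baseline term. Without that term the median was 0.1 to 0.3 m, and the largest move in 2,400 comparisons was 4.5 m.

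**The case against.** The strongest reply is that little depends on this. The trial is non-confirmatory, both criteria use Week 16, and protocol 3.1 judges the walking endpoint on Weeks 8 and 16. No decision rule is attached to Weeks 24 or 32. The event must be an unplanned leg bypass after day 113 in a patient who then walks at follow-up. Planned major surgery and critical limb ischaemia are excluded at entry, so this is probably rare. The illustration is also favourable to the concern: it mostly assumes a gain, present at both late visits. A walk soon after surgery could be worse, and surgery after day 169 touches only Week 32. All of that stands, and it sets the weight of the point. It does not remove the gap.

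One could also say that keeping or dropping walks after an intervention is a choice of estimand. That is true in general, but the plan has already chosen to drop them for the other two procedures and for an early bypass.

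A reader might infer more than the text supports:

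- *That every walk after a bypass is kept, so the primary result is biased.* SAP 6.1.3.1 censors a leg bypass before Week 16.
- *That SAP 6.1.1 and 6.1.3.1 contradict each other.* They can be applied together; they leave one case uncovered.
- *That a late conclusion has a 1.5 to 9.0% chance of changing.* In the simulation, whether the lower 80% limit exceeded 0 at Week 24 or 32 changed in that share of runs. Every run contained the event, and the SAP makes no criterion of that limit at those visits.

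**Conclusion.** The gap is real and minor. Followed as written, the SAP retains walks after a leg bypass later than Week 16 and removes walks after a leg stent or angioplasty at the same time, for both walking endpoints and without a stated reason.

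The effect is confined essentially to the Week 24 and 32 durability estimates. Under the assumed 100 to 150 m change in one patient among 20, that arm's mean moves by 5.0 to 7.5 m at visits after surgery, in either direction. It is 0 if no such case occurs. The Week 16 criteria are essentially unaffected when that patient's Week 16 walk is present; if it is missing, the Week 16 difference moves by about 2 to 2.5 m for a 100 m change. These figures are conditional illustrations, since the documents give neither a rate of late bypass nor its effect on walking.

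**What to change.** By SAP amendment before database lock:

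1. **SAP 6.1.1.** Replace the stent and angioplasty bullet with one list and one anatomical scope, for example: *any 6MWT performed after a post-baseline lower-extremity vascular intervention (bypass surgery, stenting or angioplasty), at any visit*. If the sponsor means coronary procedures to count, the rule should cover coronary stent, angioplasty and bypass alike. Otherwise the same asymmetry returns for the heart.
2. **SAP 6.1.3.1.** Separate censoring from replacement. Censoring follows the SAP 6.1.1 list at any visit; the Week 16 limit stays for replacement only.
3. **Record the change.** Protocol 11.4.3 has the same Week 16 limit, so extending censoring beyond it is a change of scope and should be logged as a change from the protocol.

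The cost is one reworded bullet, one split sentence and one line in the record of changes. Sample size, interval level and decision criteria stay as they are. Writing the rule down now also avoids settling a late-bypass case ad hoc: protocol 6.4 and SAP section 3 let the clinical team see unblinded interim results.

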6.1.2 Descriptive analyses

Maximum walking distance (MWD) and change from baseline in MWD will be listed by treatment, subject and visit. Summary statistics will be provided for raw and change from baseline by treatment and visit/time and will include sample size, mean (arithmetic), SD, median, minimum, maximum.

6.1.2.1 Graphical presentation of results

Arithmetic mean (80% CI) of raw MWD and change from baseline in MWD will be plotted by visit and treatment. Spaghetti plots of raw MWD and change from baseline in MWD of all individuals will be given by treatment.

6.1.3 Statistical model, assumptions and hypotheses

The change from baseline in MWD will be analyzed in a repeated measure mixed effects model with treatment, visit and the treatment-by-visit interaction as fixed effects and baseline MWD as a covariate. The visit-by-baseline MWD interaction may be included in the model as an additional covariate. An unstructured residual covariance structure will be used, if possible, otherwise if an unstructured covariance cannot be fitted, simpler structures will be explored.

The Least-Squares Mean (LSM) change from baseline in MWD for each visit will be estimated from the model for each treatment along with the treatment difference and the associated p-value and two-sided 80% confidence interval (CI).

From the Week 16 quantities, the following criteria will be assessed:

1. The lower confidence limit of the 80% CI for the treatment difference (LLG783 - placebo) is greater than 0.
2. The estimated treatment difference is greater than or equal to 50 meters.

The first criterion will address whether, with high certainty, LLG783 is superior to placebo in improvement in MWD. The second criterion will address whether the observed mean

improvement in MWD over placebo is at least 50 meters, a threshold that is considered to represent highly competitive efficacy in this subject population.

6.1.3.1 Model checking procedures

Handling of missing values/censoring/discontinuations

The primary analysis will be based on all subjects with a baseline MWD and at least one post baseline MWD. Subjects who undergo any lower extremity vascular interventions (angioplasty, stenting, or bypass surgery) before the Week 16 efficacy assessment or subjects who drop out for other reasons before this assessment may be replaced to ensure 40 subjects complete this primary endpoint assessment. Data from such subjects will be included in the model for the primary analysis until the time of dropout or intervention; no imputation of the missing data will be performed for the primary analysis.

6.1.3.2 Graphical presentation of results

Model estimated treatment means and difference in change from baseline in MWD will be plotted over time, by visit (all treatment groups in the same graph).

6.1.3.3 Sensitivity analyses

As sensitivity analyses, the same analysis described for the primary analysis will be performed using the last observation carried forward (LOCF) and worst observation carried forward (WOCF) approaches of imputation for missing MWD data.

Baseline maximum walk distance will be summarized separately for subjects who complete the 6MWT at week 16 and those who drop out of the study prior to this assessment. Summary statistics will include n, mean, SD, minimum, median, and maximum. The p-value from a two-sample t-test comparing the baseline maximum walk distance between the two groups will be reported together with the summary.

The relationship between the maximum change in maximum walk distance and baseline maximum walk distance will be explored using a graphical and modeling approach. A simple linear regression line and the Pearson correlation, both for each treatment, will be overlaid onto a scatterplot. Additionally, a linear regression model for the maximum change in maximum walk distance with effects of treatment, baseline, and the treatment-by-baseline interaction will be fitted, and the p-value for the test of the interaction effect will be reported.

The relationship between change in maximum walk distance and change in ABI at week 16 will be explored in a similar fashion.

Depending on the assessment of the PK profiles and dose response of subjects on different dose levels (if any after IA1), it might be reasonable to assume same mean response for both doses (providing similar AUC in the PAD population as observed in healthy volunteers). In that case different dose levels can be combined in one treatment arm regardless of different dose level.

